
We have been approved for funding by Department of Defense (DoD) to support for a 4-year multicenter RCT of TH+NMB for 48h vs. standard of care with contract to be completed June 1, 2020 and with enrollment to begin in Fall of 2020. This study was designed prior to the onset of COVID-19, which is now the most common cause of ARDS and will likely continue to be in the Fall, 2020 and perhaps beyond. Therefore, it is important to decide whether patients with COVID-19 ARDS should be enrolled in our CHILL trial. Therefore, we will conduct a 20-patient pilot safety and feasibility trial of our CHILL TH+NMB treatment vs. control in COVID-19 patients with ARDS who meet the inclusion/exclusion criteria of our DoD-funded trial. The major objective of the proposed pilot trial is to determine whether it is safe and feasible to include patients with COVID-19 ARDS in our Phase IIb CHILL RCT of TH+NMB vs. control in patients with moderate to severe ARDS.

The pilot will be conducted at the University of Maryland Medical Center. To facilitate randomization within the inclusion window, we will consent and enroll based on partial fulfillment of randomization criteria and randomize once all criteria are met. Patients will be

eligible for enrollment when they have been diagnosed with COVID-19 by PCR, and have met all Berlin criteria for moderate to severe ARDS within the 48h inclusion window except the P/F ratio  $\leq 200$  but will not be randomized until P/F ratio (measured or imputed based on SpO2) is  $\leq 200$  (while on  $\geq 8$  cm H2O PEEP and  $\geq 0.6$  FiO2). We plan to randomize a total 20 patients over 4 months to hypothermia (core temperature 34°-35°C for 48h) plus NMB or usual temperature management. The primary outcome measures will be effectiveness of cooling in achieving and maintaining the target temperature and safety measures. Secondary outcomes will include 28-day ventilator-free days (VFDs), 28-day ICU-free days, oxygen saturation index (OSI), driving pressure, Sequential Organ Failure Assessment (SOFA) score, 60-day and 90-day survival, 90-day functional assessment, cognitive assessment at ICU and hospital discharge, and biomarkers of inflammation and lung injury. Since the nature of the intervention precludes blinding, all treatment and clinical decision making related to study outcomes will be protocolized and compliance with study protocols will be monitored.

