### 3.3/ Randomization

Subjects will be stratified by proning status at enrollment and randomized within each stratum to receive TH or usual temperature management using a 1:1 assignment ratio. Treatment group assignment will be made using an Excel-based assignment tool stored on the UMB Microsoft OneDrive, which records date, time, and investigator who makes the treatment assignment. Baseline APACHE II, Sequential Organ Failure (SOFA) score 3, driving pressure, P/F ratio, and oxygen saturation index will be documented at time of randomization to assess comparability of disease acuity between groups.

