### 7.2/ Ventilatory and respiratory parameters

Ventilatory and respiratory parameters ( Peak Airway Pressure (Ppeak), Airway Plateau Pressure (Pplat), Positive End Expiratory Pressure (PEEP) and Mean Airway Pressure ( $P_{\overline{aw}}$ ) will be obtained from standard of care mechanical ventilation record. Driving Pressure is calculated as the difference between airway plateau pressure and end-expiratory pressure (Pplat – PEEP) during a breath without spontaneous ventilator effort and Oxygen saturation index (OSI). This will be calculated as the product of mean airway pressure, fraction of inspired oxygen, and 100, divided by pulse oxygen saturation ( $P_{\overline{aw}} \times FIO_2 \times 100/SpO_2$ ) will be calculated and recorded per study data collection requirements.

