**Respiratory Parameters:**

 For the 24 hours preceding randomization, record the lowest measured post-intubation SpO2 date and time of measurement, and the Mean Airway Pressure, measured PEEP, and FiO2 from the nearest time relative to the lowest SpO2 measurement. Record the post-intubation ABG with the lowest PaO2, the date and time that the ABG sample was collected and the Mean Airway Pressure, and FiO2 measured PEEP from the nearest time relative to that ABG. If no ABGs were done, check the None box.

**SpO2:** Lowest SpO2:    %  
 Date/Time of SpO2 measurement:    /   /        
MONTH D D Y Y Y Y TIME (0-2400)

Corresponding Mean Airway Pressure:   cm H2O  
 Corresponding Measured PEEP:   cm H2O  
 Corresponding FiO2:    %

**ABG:** Lowest PaO2:    mm Hg  
 pH:  .   pCO2:    mm Hg  
 Date/Time of ABG collection:    /   /        
MONTH D D Y Y Y Y TIME (0-2400)

Corresponding Mean Airway Pressure:   cm H2O  
 Corresponding Measured PEEP:   cm H2O  
 Corresponding FiO2:   %

None

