Pilot Randomized Clinical Trial of Therapeutic Hypothermia Plus Neuromuscular Blockade vs. Standard of Care in Patients With Moderate to Severe ARDS - the Cooling to Help Injured Lungs (CHILL) Pilot Study

NCT03376854

Statistical Analysis Plan

Date: May 19, 2020

Statistical Analysis Plan: This is a pilot study of feasibility to demonstrate feasibility and safety to treat patients with COVID-19 and ARDS with our CHILL treatment protocol (hypothermia to core temperature 34-35°C + NMB for 48h) and to determine whether there are any trends toward benefit in the treated group. The primary outcome will be analyzed using descriptive statistics, the mean \pm SD and the median \pm IQR of time to reach the target temperature and the percent of total treatment time within the targeted temperature range. Differences in SAEs will be analyzed by Chi square. The group difference on 28-day VFDs will be tested with a permutation test for the difference in group means with alpha = .05 (two-tailed). This test was chosen due to the large number of zero values expected (based on our open-label pilot and retrospective studies). If the difference on a baseline prognostic variable is statistically significant, we will perform a secondary analysis to adjust for this variable using a regression approach. For secondary clinical outcomes t-tests, Wilcoxon, or chi-square tests will be used as appropriate. Mixed model repeated measures ANOVA will be used to test for group differences for physiological and biomarker secondary outcomes over days 0, 1, 2, 3, 4, and 7. We will not include an interim analysis in this small RCT with only 20 subjects.

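### The only adjusted VFD analysis is run if a baseline test is significant, which at 10 per arm takes an imbalance of about 0.94 SD (two-sided 0.05 t-test assumed)

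*SAP*

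**What the plan says.** The SAP compares 28-day VFDs between arms with a permutation test on the means, two-sided at 0.05. Its reason for that choice is: "This test was chosen due to the large number of zero values expected". The next sentence adds the adjusted analysis: "If the difference on a baseline prognostic variable is statistically significant, we will perform a secondary analysis to adjust for this variable". The adjustment is to be by regression of an unspecified kind. The SAP does not list the prognostic variables and gives no test or level for the baseline comparison; the 0.05 is stated for VFDs only. There is no adjusted VFD analysis outside this trigger, and the randomization stratum is not mentioned.

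The sample size is 20 in both documents (SAP: "We will not include an interim analysis in this small RCT with only 20 subjects"; Protocol 1.1: "We plan to randomize a total 20 patients over 4 months"). Protocol 3.3 randomizes 1:1 within strata of proning status. It also plans to compare disease acuity between the arms at baseline, using APACHE II, SOFA and three respiratory measures: "driving pressure, P/F ratio, and oxygen saturation index will be documented at time of randomization". Protocol 1.1 lists VFDs as a secondary outcome, although Aim 2 in section 1.2 calls them primary among the efficacy measures.

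**The concern.** Under proper randomization every baseline difference is due to chance. At the 0.05 level the trigger therefore fires about 5% of the time per variable, whether or not that variable predicts outcome. What distorts a VFD comparison is the size of the imbalance multiplied by the strength of the covariate's relation to VFDs, and a baseline p-value does not measure that product. In 20 patients most sizeable imbalances will not be significant.

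Because no variable is named, both the decision to adjust and the choice of covariate are made after the baseline data are seen, in a trial that cannot be blinded. The SAP wants to look for trends toward benefit. With so few patients, a chance difference in severity is the obvious rival explanation for a trend, and in most trials where a reader would raise it the plan offers no adjusted estimate to set beside the unadjusted one.

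**Working it through.** The documents give no detectable-imbalance or power figure, so there is nothing of theirs to reproduce.

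**Inputs.** From the documents: 20 patients at 1:1, hence about 10 per arm. Assumed, because the documents are silent: a two-sided t-test at baseline with alpha 0.10, 0.05 or 0.01; one continuous covariate; a covariate-outcome correlation r of 0.3, 0.5 or 0.7.

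**Imbalance needed to trigger adjustment.** The threshold is t(1 − alpha/2, 18) × √(2/10), in SD units. A chance imbalance, in units of the true SD, is distributed N(0, 0.2), so P(above 0.5 SD) = 0.264.

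| alpha | t quantile | threshold (SD) | P(imbalance between 0.5 SD and threshold) |
|---|---|---|---|
| 0.10 | 1.734 | 0.775 | 0.181 |
| 0.05 | 2.101 | 0.940 | 0.228 |
| 0.01 | 2.878 | 1.287 | 0.260 |

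Uneven arms change little: at 0.05 the threshold is 0.944 for 11 vs 9 and 0.959 for 12 vs 8. A binary covariate is no easier; 2/10 vs 8/10 is needed by Fisher's exact test.

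The last column sets a true-SD imbalance against a sample-SD threshold. In 200,000 simulated trials, with the imbalance in true SD and each t-test using its own estimated SD, 21% of trials exceed 0.5 SD and stay unadjusted: 0.2125/0.264, or about 80% of all such imbalances. With both in sample SD the figures are 22.7% out of 27.7%, or 82%.

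**Shift in the VFD difference.** Shift = imbalance × r. For imbalances of 0.5 to 0.94 SD, in either direction:

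- r = 0.3: 0.15 to 0.28 outcome SD
- r = 0.5: 0.25 to 0.47
- r = 0.7: 0.35 to 0.66

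To put this in days I assumed 40%, 50% or 60% zeros and the rest uniform on 1 to 25 days (SD 7.8 to 8.5 days), with r as the latent correlation. The mean shift in the unadjusted trials beyond 0.5 SD is then 1.2 to 1.6 days at r = 0.3, 2.1 to 2.5 at r = 0.5 and 3.0 to 3.6 at r = 0.7.

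**Precision.** For a normal outcome and one covariate, always adjusting multiplies the variance of the treatment estimate by (1 − r²) × 17/16:

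- r = 0.3: 0.91 × 1.0625 = 0.967
- r = 0.5: 0.75 × 1.0625 = 0.797

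Simulation (60,000 trials) gives 0.972 and 0.798 for always adjusting, against 0.996 and 0.952 for adjusting only on the trigger. With zero-heavy VFDs, always adjusting gives 0.98 to 1.00 at r = 0.3 and 0.86 to 0.88 at r = 0.5; the trigger gives about 1.00 and 0.97.

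**Check of the proposed remedy.** VFDs are regressed on stratum and covariate without treatment, and treatment is then permuted within stratum on the residuals. With two strata of 10 and 40% or 60% zeros, type I error is 4.0 to 6.0% (2,500 trials per setting, Monte Carlo SE 0.4 points). Power at a latent shift of 1 SD, unadjusted vs adjusted:

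- 40% zeros: 50% vs 54% (r = 0.3), 50% vs 59% (r = 0.5)
- 60% zeros: 47% vs 49% (r = 0.3), 47% vs 53% (r = 0.5)

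**The case against.** The strongest reply is that little hangs on this. The unadjusted comparison is unbiased over repeated randomizations, and the permutation test already allows for chance imbalance. At the SDs assumed above, the standard error of the VFD difference is 7.8 to 8.5 × √0.2 = 3.5 to 3.8 days, so every average shift quoted is about one standard error or less, and under half of one at r = 0.3. The zero fractions and correlations are my assumptions, not figures from the documents. All of this stands and keeps the point minor.

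Second, Protocol 3.3 does name five acuity measures for comparing the arms, so an imbalance need not go unseen. That is true, but the SAP does not make them its adjustment set, and seeing an imbalance does not supply an adjusted estimate.

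Third, adjustment may gain little, and the one-covariate variance factor is not that of a model with stratum added. At r = 0.3 and with a non-prognostic stratum, the two-term model gives about 0.976 if the stratum is balanced between arms and 1.04 if it is imbalanced by chance. Stratified randomization aims at the former, although the documents do not describe blocking. The stronger argument for the change is prespecification rather than power.

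Fourth, the choice of oxygen saturation index (OSI) is open to argument. A qualifying P/F value, measured or inferred, is recorded before randomization, and the baseline form holds SpO2 and mean airway pressure at two points: the worst in 24 hours and the most recent. This does not rescue the trigger, but it means the SAP must say which values enter the index.

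**Conclusion.** The point holds as a low-priority improvement. The SAP's only adjusted VFD analysis depends on a baseline significance test with no named variable, test or level. For a two-sided 0.05 t-test at 10 per arm, the trigger needs an imbalance of 0.94 SD (0.78 to 1.29 SD across alpha 0.10 to 0.01). It would miss roughly four in five chance imbalances above 0.5 SD, which is 21 to 23% of all trials for one continuous covariate. It also forgoes most of whatever precision adjustment could bring: at r = 0.5 with a normal outcome, the variance falls by about 5% instead of 20%. The size of any VFD shift rests on assumed correlations and, for days, on an assumed VFD distribution. The main permutation test is not in question, and the pilot's feasibility and safety conclusions are not affected.

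**What to change.** Delete the significance trigger and keep the unadjusted permutation test as the main VFD analysis. Name now one supportive adjusted analysis, to be run whatever the baseline data show, containing treatment, proning stratum and one baseline severity measure.

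OSI is a workable choice. Protocol 7.2 defines it ("calculated as the product of mean airway pressure, fraction of inspired oxygen, and 100, divided by pulse oxygen saturation"), and the Respiratory Parameters item of the Baseline Data form records SpO2, FiO2 and mean airway pressure together. Measured P/F from that form can be missing ("If no ABGs were done, check the None box"). State which recorded set is used, for example the lowest post-intubation SpO2 in the 24 hours before randomization with the nearest FiO2 and mean airway pressure.

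Keep a permutation p-value because many zeros are expected. One option is the method checked above: regress VFDs on stratum and OSI without treatment, then permute treatment within stratum on the residuals. Show baseline balance descriptively, without p-values.

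The cost is SAP wording and one or two degrees of freedom in one supportive model; no new data are needed. If OSI is only weakly prognostic (r = 0.3), the gain in variance is about 0 to 3% with the stratum balanced, and a chance imbalance in the stratum could turn it into a small loss.

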### 1.2/ Study Aims and Objectives

We will conduct the CHILL-pilot single-center RCT of TH in patients with COVID-19 and ARDS with P/F < 250 to address the following specific aims:

1. **Aim 1: Analyze the safety and feasibility and the potential lung protective effect of treating patients with COVID-19 infection and ARDS with P/F < 200 with mild TH (core temperature 34°-35°C) + NMB for 48h compared with controls receiving standard temperature management.** We expect the TH-treated group to achieve targeted temperature within 4h of randomization and to maintain TH for 48h without significant increase in serious adverse effects compared with the control arm.
2. **Analyze the potential lung protective effect of mild TH (core temperature 34°-35°C for 48h) and NMB in patients with ARDS and P/F < 200 compared with controls receiving standard temperature management.** We expect the TH-treated group to trend toward having more 28-day VFDs (primary) and 28-day ICU-FDs, and improved day-3 driving pressure and OSI than the controls.
3. **Evaluate the effects of TH on systemic inflammation and extrapulmonary organ dysfunction.** We expect the treated group to have reduced levels of proinflammatory mediators and lower Sequential Organ Failure (SOFA) scores than controls.

The proposed pilot study will determine whether we can safely include patients with COVID-19 and ARDS in our larger Phase IIb trial of TH and NMB in patients with ARDS. It will help us determine whether the 48h duration of cooling is sufficient.

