### 5/ Subject Enrollment and Randomization Procedures

If the patient meets the P/F ratio criterion for randomization (from ABG or imputed from SpO2), they will be randomized simultaneously with enrollment. Otherwise their P/F ratio will be followed until it is <200 or they exit the 48h ARDS window. If the patient meets the P/F ratio criterion within the ARDS window, mark the “Yes” box about randomization on line 12, otherwise check the “No” box. If the patient is randomized, collect the baseline blood sample, obtain the treatment assignment using the on-line assignment tool, enter the randomization date and time on line 14 and the treatment assignment on line 15. Once Randomized, baseline information will be recorded on the Baseline Data CRF and, if assigned to the Therapeutic Hypothermia arm, sedation, NMB, and cooling will begin as soon as possible.

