### Placing the order to initiate hypothermia:

- Order sedation to RASS >-4 and Nimbex to achieve 2 twitches on train-of-four testing.
- Enter UMMC MED-CC Hypothermia Following Arrest Supplemental order set in Epic with the following modifications:
  - i. De-select: Capnography, CVP monitoring, SvO2 monitoring, NPO, Bair Hugger, Maintain MAPBP > 80 mmHg, Document Water temperature, CXR, sodium chloride 0.9% bolus, fentanyl, and vecuronium, cisatracurium.
  - ii. Under Chemistry, select Comprehensive Metabolic Panel
  - iii. Modify Hyper/Hypothermia order by changing stop date from 24h to 48 h and changing comments to: "Lower patient's temperature to **34 – 35C** as quickly as possible per protocol. Maintain **core temperature between 34 and 35C for 48 hours**. AT **48 hrs** after the initial cooling, re-warm patient no faster than **0.3** degree C per hour to **36C**." Delete "Then maintain ≤ 37C for 48 hours." (Changes from Epic order set are underlined and bolded.) These instructions have been added to the Randomization CRF.

2. Usual Temperature Management Arm: Controls will receive sedation and NMB as clinically indicated to achieve synchrony with the ventilator. During the 54h post-randomization period (corresponding with cooling and rewarming in the TH arm), acetaminophen will be given for core temperature  $>38^{\circ}\text{C}$  and surface cooling initiated for core temperature  $>38.5^{\circ}\text{C}$  and adjusted to maintain temperature  $\leq 38^{\circ}\text{C}$ . If patients are hypothermic (core temperature  $<35.5^{\circ}\text{C}$ ), surface warming will be initiated to restore core temperature to  $37^{\circ}\text{C}$ . Following the 54h treatment period, temperature management in both arms will be directed by the ICU team.

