**eTable 2: Imputed PF ratio (cells) for combinations of SpO2 (rows) and FiO2 (columns)**

	0.30	0.35	0.40	0.45	0.50	0.55	0.60	0.65	0.70	0.75	0.80	0.85	0.90	0.95	1.00
80%	148	127	111	98	89	81	74	68	63	59	55	52	49	47	44
81%	151	129	113	101	91	82	76	70	65	60	57	53	50	48	45
82%	155	132	116	103	93	84	77	71	66	62	58	55	52	49	46
83%	158	136	119	106	95	86	79	73	68	63	59	56	53	50	47
84%	162	139	122	108	97	89	81	75	70	65	61	57	54	51	49
85%	167	143	125	111	100	91	83	77	71	67	63	59	56	53	50
86%	171	147	129	114	103	94	86	79	73	69	64	61	57	54	51
87%	177	151	132	118	106	96	88	81	76	71	66	62	59	56	53
88%	182	156	137	121	109	99	91	84	78	73	68	64	61	58	55
89%	189	162	141	126	113	103	94	87	81	75	71	67	63	60	57
90%	196	168	147	130	117	107	98	90	84	78	73	69	65	62	59
91%	203	174	153	136	122	111	102	94	87	81	76	72	68	64	61
92%	213	182	159	142	128	116	106	98	91	85	80	75	71	67	64
93%	223	191	168	149	134	122	112	103	96	89	84	79	74	71	67
94%	236	202	177	157	142	129	118	109	101	94	89	83	79	75	71
95%	252	216	189	168	151	138	126	116	108	101	95	89	84	80	76
96%	273	234	205	182	164	149	136	126	117	109	102	96	91	86	82

Conditions required to use inferred P/F ratio include: (a) SpO2 values 80-96%, (b) SpO2 measured ≥10 min after FiO2 change, (c) PEEP ≥ 8 cm H2O, (d) adequate pulse oximeter wave form, and (e) qualifying inferred P/F ratio is confirmed 1-6 hrs after the initial determination.

P/F ratio criterion met within 7 ventilator days

- Yes Collect **baseline blood sample**, randomize and record randomization time and treatment assignment below
- No STOP

Is this patient currently receiving prone positioning alternating with supine positioning?

- Yes
- No

Randomization date/time:    /   /          
MONTH D D Y Y Y Y TIME (0-2400)

Treatment assignment (check one)

- Therapeutic Hypothermia
- Usual Treatment

Initiate sedation, NMB, and cooling protocol for subjects randomized to Therapeutic Hypothermia

Complete Baseline information CRF.

See schedule for first week blood and data collection below.

--	--

[figure not shown]
SITE ID

--	--	--	--

PATIENT ID

--	--	--

LETTER CODE

- Collect baseline blood and complete Baseline CRF based on 24h preceding randomization
- Collect day 1 blood and complete Day 1 CRF at 0800 on randomization day + 1; (the duration of day 1 may be 8h 1 min to 31h 59 min as indicated by the examples a - c)

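### The repeated-measures ANOVA pools pre-treatment day 0 with five post-randomization days but names no baseline adjustment and no tested term; adjusting for day 0 is a near-free gain for these secondary outcomes

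*SAP*

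**What the plan says.** The SAP gives one sentence to these outcomes: "Mixed model repeated measures ANOVA will be used to test for group differences for physiological and biomarker secondary outcomes over days 0", and the list continues with days 1, 2, 3, 4 and 7. It names no model term, contrast or time point, no baseline covariate, and no constraint that the arms share a mean at day 0.

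The protocol shows that day 0 precedes treatment:

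- Section 5 orders the steps for blood: "If the patient is randomized, collect the baseline blood sample, obtain the treatment assignment using the on-line assignment tool".
- The appended Screening/Enrollment/Randomization Source Document gives the window: "Collect baseline blood and complete Baseline CRF based on 24h preceding randomization".
- Section 3.3 lists APACHE II, SOFA, driving pressure and P/F among the baseline measures, and ends "oxygen saturation index will be documented at time of randomization to assess comparability of disease acuity between groups". The stated purpose is comparability, not adjustment.

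The SAP's only adjustment rule is conditional: "If the difference on a baseline prognostic variable is statistically significant, we will perform a secondary analysis to adjust for this variable". It follows the ventilator-free-days (VFD) test and is not tied to the repeated-measures model. Two further passages bear on the model. Section 3.3 says "Subjects will be stratified by proning status at enrollment and randomized within each stratum", and Aim 2 in section 1.2 expects "improved day-3 driving pressure and OSI than the controls". The SAP sets up neither a stratum term nor a day 3 contrast.

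**The concern.** Randomization makes the true group difference at day 0 zero. A test that averages the group difference over all six days therefore mixes five days that can carry an effect with one that cannot. With about 10 patients per arm, chance differences at day 0 are large, and without adjustment they pass into the estimated treatment effect. The SAP wants to see trends toward benefit, so a shifted or diluted estimate on these outcomes could mislead planning for the larger trial. Because the tested term is not named, a reader cannot tell whether this happens. In an unblinded study, the term could also be chosen after the data are seen.

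**Working it through.** **Inputs.** 20 patients (SAP), 1:1 allocation (Protocol 3.3), so about 10 per arm. Six days are listed, five of them after randomization. The documents give no effect size, SD or within-patient correlation for these outcomes, and no planned power to reproduce. Two-sided 5% is stated only for VFDs and is assumed here. Also assumed: unit SD, complete data, effect 0.8 SD, and correlation r = 0.3/0.5/0.7 under compound symmetry (CS) or AR1 over the actual days.

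**1. Dilution.** For a constant effect d, the six-day group difference has expectation (0 + 5d)/6 = 0.83d. For d = 0.8 this is 0.67.

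**2. Closed-form power under CS.** The variance of a patient's summary measure is:

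- six-day mean: (1+5r)/6 = 0.417/0.583/0.750
- five-day mean, unadjusted: (1+4r)/5 = 0.44/0.60/0.76
- five-day mean, adjusted for day 0: (1+4r)/5 − r² = 0.35/0.35/0.27

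At r = 0.5, the six-day main effect has SE √(2×0.583/10) = 0.342, so 0.667/0.342 = 1.95 on 18 df, and power is 46%. The adjusted average has SE √(2×0.35/10) = 0.265, so 0.8/0.265 = 3.02 on 17 df, and power is 81%. Dropping day 0 without adjusting gives 72/59/49% across the three correlations, which lies between the two.

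**3. Simulated power** (40,000 trials per cell, baseline slope estimated, which costs about two points against the closed form):

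| Effect, covariance | Main effect, six days | Adjusted day 1-7 average |
|---|---|---|
| Sustained 0.8 SD, CS | 59/46/37% | 79/79/88% |
| Sustained 0.8 SD, AR1 | 80/66/50% | 87/79/73% |
| Transient, CS | 26/20/17% | 39/38/47% |

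The transient pattern is 0.5, 1, 1, 0.5 and 0 times 0.8 SD on days 1, 2, 3, 4 and 7. The adjusted average beat the main effect in all 12 cells (two effects, two covariances, three correlations). For the transient effect under CS, the group-by-day test has 32/43/68%, better than the adjusted average at r = 0.5 and 0.7.

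**4. Chance imbalance.** The SE of a day 0 difference is √(2/10) = 0.447 SD. Significance needs 2.101 × 0.447 = 0.94 SD. About 21% of trials carry a non-significant day 0 imbalance above 0.5 SD on a given outcome. In those trials, with no true effect, the mean shift in the estimate is:

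| Covariance | Six-day main effect | Day 0 dropped, unadjusted | Baseline-adjusted |
|---|---|---|---|
| CS | 0.28/0.39/0.50 SD | 0.20/0.33/0.46 SD | about 0 |
| AR1 | 0.16/0.21/0.31 SD | 0.06/0.13/0.25 SD | about 0 |

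Under CS, 0.20/0.28 = 71%, 0.33/0.39 = 85% and 0.46/0.50 = 92% of the shift remains when day 0 is dropped. Under AR1 the shares are 38%, 62% and 81%.

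**5. Error rate.** Unconditional type I error of the main effect and of the adjusted average is 4.8-5.1%. Within the imbalanced trials of step 4, the main effect rejects in 7.4-9.6% and the adjusted average in 4.9-5.3%.

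**The case against.** The strongest reply is that the harm depends on a reading the SAP does not state. A difference between groups over days can equally mean the group-by-day interaction, which compares each arm's course from its own day 0 and is neither diluted nor distorted in this way. Section 8 limits managed temperature to about two days ("During the 54h post-randomization period (corresponding with cooling and rewarming in the TH arm"), so a transient effect is plausible, and for that the interaction can be the stronger test. This stands. A reader might infer that the SAP tests a diluted main effect, or that listing day 0 as a response is an error. The documents support neither, because no term is named and day 0 as a response is valid under several standard models.

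It is also fair that most of the CS shift comes from not adjusting, which is true of any unadjusted comparison, rather than from including day 0. The conditional adjustment rule is weak evidence about this model because the SAP does not tie the two together. The 0.5 SD cut-off is only illustrative. A reader might further infer an inflated false-positive rate. Overall it is not inflated for a single fixed test, and even in the imbalanced trials it stays below 10%.

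What remains is that the day 0 value is collected anyway, the better method is known, and the plan does not specify it.

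**Conclusion.** The point holds as an improvement to the analysis, not as proof of an invalid test. For a sustained 0.8 SD effect, adjusting for day 0 in place of the six-day main effect gains about 20/33/51 percentage points of power under CS (79−59, 79−46, 88−37) and 7/13/23 under AR1 (87−80, 79−66, 73−50). It also removes the chance-imbalance shift. If the sponsor intends a group-by-day test, the loss described here does not arise, but the SAP has to say so.

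These sizes rest on assumed effect, correlation and covariance, 10 per arm and complete data. Deaths and extubation will thin the later days. Only physiological and biomarker secondary outcomes are touched; the feasibility and safety outcomes and the VFD permutation test are not. The change should be made, but it is of moderate weight in a 20-patient pilot.

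**What to change.** Replace the SAP sentence with:

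> Physiological and biomarker outcomes on days 1, 2, 3, 4 and 7 will be analysed with a mixed model with fixed effects for treatment, day, treatment-by-day, day 0 value and proning stratum. The tested term is the baseline-adjusted treatment difference averaged over days 1-7. Day-specific adjusted differences with 95% CIs, including day 3 for driving pressure and OSI, and the number of patients contributing on each day will be reported.

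- **Alternatives.** A model with day 0 as a response and one day 0 mean common to both arms is equivalent and keeps patients who lack a day 0 value. If a transient effect is expected, the joint treatment-by-day test may be named instead, before data are seen.
- **Covariance.** Use a parsimonious structure with a small-sample degrees-of-freedom correction such as Kenward-Roger. An unstructured 6×6 matrix has 6×7/2 = 21 parameters for 20 patients. A simple structure without a correction is not safe either: in a simulated check, a spatial-power fit to CS data rejected a true null in 8.4/6.9/4.2% of trials for the average.
- **Day 0 value.** Name the Baseline CRF field for each outcome and match it to the daily measure. The form holds the lowest SpO2 of the preceding 24 h (line 15), the most recent values (line 22) and post-change plateau pressure and PEEP (line 24), whereas the day 1 to 4 forms take the lowest SpO2 per 2-hour block.

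The cost is wording and one or two model degrees of freedom, with no new data. Missing values after extubation or death are not solved; section 10.5, for example, collects plateau pressure only while the patient is intubated.
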